
4. Study Population: Describe the characteristics of the participant population including, anticipated number, age range, gender, ethnic background and health status. Provide a candid discussion of potential problems related to the study population. Explain the rationale for the use of special classes such as fetuses, pregnant women, children, prisoners, or other vulnerable populations. If women, minorities or children are excluded, provide written justification.

a. Anticipated number of participants to be enrolled:
 
Aim 3: We will recruit a total of 142 patients to allow for approximately 10% attrition from each group. The final number of enrollees we require to successfully complete the study is 128 LACDHS patients composed of 32 African American and 96 Latinx patients who have not completed COVID-19 testing and/or vaccination, according to LACHDS records.
 
Each arm will have at least 64 LACDHS patients, comprised of at least 16 African American and 48 Latinx patients who have not completed COVID-19 testing and/or vaccination

b. Age range: 16 years old and older for Aim 3

c. Gender: all genders for Aim 3

d. Racial/ethnic background: African American and Latinx for Aim 3

e. Describe health status: LACDHS patients who did not complete a lab order for COVID-19 testing or COVID-19 vaccination from Aims 1 and 2

f. Foreign language translation and interpreter required? None

g. Other population characteristics: None

h. Potential problems related to study population: None

i. Vulnerable populations included in the study and the rationale: None

j. If excluding women, minorities, and children, please provide justification:
 
We will exclude children (those under the ages of 16) from this study.
 
Moreover, we are excluding patients under the age of 16 because a) they were not yet eligible for COVID-19 vaccination as of April 19, 2021 and b) decision making on COVID-19 testing and vaccination for children is usually made by their adult caregivers.

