Our study staff will contact the patients via telephone, ascertain their self-reported eligibility to participate in the study, present the study and invite them to participate in our 6-week study, where they will be randomly assigned to one of two groups. The study staff will explain what will be required of the participant, and answer any questions the potential participant may have about the study. If participants agree to be in the study, the study staff will send the participant a copy of the consent forms and follow up with them at a separate time to provide them time to review the consent forms with family or friends. During the phone call, the study staff will notify the participant they will be randomly assigned to one of two following groups:

- Group 1 (Control Arm): will consist of two phone calls where participants are to complete a total of 4 surveys (demographic, pre-study and post-study survey, and CDE survey). The pre- and post- surveys will be completed six weeks apart at a time that is convenient for them.
- Group 2 (Intervention Arm): in addition to the surveys listed in Group 1, the group will consist of a six-week COVID-19 educational program, where participants will participate in a weekly 1.5 - 2-hour virtual classroom, and weekly 30-60 minute personal session with an assigned and IRB-approved Intervention CHW.
 - o Only the weekly group session will be recorded for further analysis and program evaluation, the personal session with the CHW will not be recorded. The Zoom recording feature asks participants to consent to being recorded. If participants do not agree to being recorded, the Zoom feature automatically disconnects the

participant from the Zoom meeting. As such, participants must agree to being recorded during the consent phone call if they are randomly assigned to this group. Therefore, we will only include one option on the consent form saying *they agree to being recorded during the weekly group only if they are assigned to Group 2.*

The approach for recruitment is based on our previous consultation with the LACDHS partners. The study staff created telephone recruitment scripts, patient recruitment flyers, and a recruitment strategy to illustrate what the study staff will be communicating with participants, and attached to the IRB application. The approaches below are overviews and will refer to the recruitment materials.

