We will utilize a randomized control design consisting of one treatment arm and a control arm. African American and Latinx patients who did not complete COVID-19 testing or vaccination will be recruited from the patient list obtained from Aim 1 data pull of the LACDHS EHR. The patient list obtained by the data pull will be filtered by the patient list provided by the LACDHS Vaccine Hesitancy Outreach Group. Based on the inclusion criteria, we will recruit a total of 142 patients to allow for approximately 10% attrition from each group. Patients who meet the inclusion criteria and agree to participate in the 2-month intervention will be randomly assigned to either the intervention or control arm.

We will stratify the randomization on the basis of race/ethnicity and we will use permuted blocks (**see table 3**). We will use a scheme such as found at randomization.com. Here we will define a block size of 4 subjects and determine a random permutation of 2 treatment and 2 control assignments employed the scheme in question. This is repeated to cover the request number of blocks in each stratum in order to randomize the total number of required subjects. We expect our study sample to reflect LACDHS patient population race/ethnicity stratification (9% African American and 68% Latinx).

Table 3 - Stratified Random Sampling

Block	Category	Number of participants to enroll
Block 1	African American + control	18
Block 2	African American + case	18
Block 3	Latinx + control	53
Block 4	Latinx + case	53

We will refer the control arm as “Group 1” and the intervention arm as “Group 2” for the purposes of explaining to prospective participants they will be randomly assigned to a group without compromising the integrity of the study.

Participants will need to complete the consenting process, complete a basic demographic survey, and wait to be randomly assigned to either Group 1 or 2. Once assigned to a group, the study staff will notify the participant of which group they were assigned to. The methodologies of

each respective group are detailed below after the participants are notified which group they were randomly assigned to.

Control Arm- Standard Treatment (Group 1):

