Aim 3 - After data cleaning, we will assess psychometric properties of all scaled measures, calculate descriptive statistics to ensure quality of the data (check distributions, examine outliers) and to describe study participants. Bivariate analyses will include independent t-tests models (or their nonparametric equivalents, e.g. Wilcoxon rank-sum test, differences between the groups in trust and self-efficacy. Paired-tests (or Wilcoxon signed-rank test) will be used to assess change within groups. Contingency table analyses will address intention to participate in COVID-19 testing and vaccination. We will then fit multiple regression models predicting change in COVID-19 testing- and vaccine-related knowledge, trust, and self-efficacy as a function of intervention group, racial/ethnic group, and possible interactions. We will use covariate adjustment approaches such as multiple linear and logistic regression models for the three outcomes (trust, self-efficacy, intent to participate) while controlling for demographic characteristics (e.g. age, gender, education, health status) and other potential covariates that will be identified a priori. We do not anticipate many missing data, given the format of completion. However, if we do have 10% or more missing, we will impute data using SAS PROC MI and SAS PROC MIANALYZE to implement these multiple imputation procedures. With respect to sample size, with 64 subjects in each of the two study groups, it will be possible to detect an effect size of 0.5 standard deviations in a quantitative outcome (a medium effect size in Cohen’s terminology) with 80% power and 2-sided 5% significance level.

VII. Funding

4. Check all types of funding sources for this study.

 Federal Grant/Contract  State, Local Government  International	 Private  Internal Grant Program  Departmental
--	--

 Industry	 Other:
2. Name of Funding Source (e.g. NIH)	NIH/National Library of Medicine
3. Grant/Contract Title*	A Community Health Worker Intervention to Identify and Decrease Barriers to COVID-19 Testing and Vaccination among Los Angeles County Department of Health Safety-Net Patients (Title of the Supplement to parent R01)

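### A single disclosed block size of 4, with recruiting staff who also announce the arm, lets anyone tracking past assignments foresee about a third of the next ones

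*Protocol*

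**What the plan says.** Section VI, item 8 (Intervention Design) of the protocol sets the allocation: "We will stratify the randomization on the basis of race/ethnicity and we will use permuted blocks". It then fixes the block: "Here we will define a block size of 4 subjects and determine a random permutation of 2 treatment and 2 control assignments". The same block is used throughout: "This is repeated to cover the request number of blocks in each stratum". No other size is given, and a public web generator is named as the kind of scheme to be used. Table 3 plans 18 + 18 African American and 53 + 53 Latinx patients, 142 in all.

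On who does what:

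- **Screening (item 7, telephone script):** "Our study staff will contact the patients via telephone, ascertain their self-reported eligibility to participate in the study". Item 7 (Identification Strategy) lists the study staff as a project coordinator and a research assistant. They filter the patient list by race/ethnicity before calling.
- **Consent (items 7 and 21):** study staff send the forms, call back later and record verbal consent.
- **Announcement of the arm (item 8):** after consent and a demographic survey the participant waits for assignment; then "the study staff will notify the participant of which group they were assigned to".
- **Outcome (items 9 and 10a):** study staff administer the post-survey by telephone.

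The protocol describes no blinding of staff and does not say who holds the list.

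**The concern.** With a known 2:2 block, the remaining places can be worked out from those already filled. Staff know each patient's stratum before the call and learn each assignment when they announce it, so they have what they need to track the blocks.

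Consent before assignment stops a patient from being withdrawn or redirected once the arm is known. It does not govern whom staff call back next, or when they complete an enrolment. Those choices come earlier and could be influenced, even without intent, by knowing which arm is next.

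Item 7 says community health workers can assess a referred patient's interest in joining and help with retention, so information about engagement may reach staff before enrolment. The arms differ sharply in what they ask: up to 20 hours against up to 2, with intervention groups starting once 5-8 patients are available. Trust, self-efficacy and intent are outcomes on which more and less engaged patients could plausibly differ at the outset.

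**Working it through.** **Plan's own figures.** The protocol gives no predictability figure, so there is none to reproduce. Its sample size does check. With "with 64 subjects in each of the two study groups", a difference of 0.5 SD and two-sided 5%, the noncentral t (126 df) gives 80.1% power against the stated 80%. Recruitment: 128/0.9 = 142.2, against the stated 142.

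**Inputs.** Block of 4 (2:2), two strata, 36 and 106 patients (item 8 and Table 3).

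**Certain assignments in one block.** There are 6 equally likely orders. Positions 1 and 2 are never certain. Position 3 is certain when the first two went to the same arm, which is 2 of 6 orders. Position 4 is always certain.

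(0 + 0 + 1/3 + 1)/4 = 1/3 = 33.3%

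**Best guess in one block** (guess the arm with more places left; toss a coin when equal):

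| Position | Probability correct |
|---|---|
| 1 | 1/2 |
| 2 | 2/3 |
| 3 | 1/3 × 1 + 2/3 × 1/2 = 2/3 |
| 4 | 1 |

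Total 2.833; 2.833/4 = 70.8%, against 50% with no information.

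**Over the planned 142.**
- African American: 36/4 = 9 full blocks, 9 × 4/3 = 12 certain.
- Latinx: 106 = 26 × 4 + 2, so 26 × 4/3 = 34.7 certain and none in the two left over.
- Certain: 46.7/142 = 32.9%.
- Best guess: (35 × 2.833 + 1/2 + 2/3)/142 = 70.7%.

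**Effect of changing block sizes.** Fixed sizes are exact. Varying sizes come from 1,000 simulated lists of 36 + 106, with sizes equally likely and staff assumed to know the set of sizes but not their order.

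| Scheme | Certain | Best guess correct |
|---|---|---|
| Fixed 4 (planned 142) | 32.9% | 70.7% |
| Fixed 6 (full block) | 25% | 68.3% |
| Fixed 8 (full block) | 20% | 66.6% |
| Random 4/6 | 5.8% | 69.0% |
| Random 4/6/8 | 2.4% | 67.8% |

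Varying the size removes nearly all the certainty but little of the guessability.

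**What steering could do (assumed sizes, not in the protocol).** Suppose staff place patients with expected outcome d SD better in known intervention places and d SD worse in known control places, at every certain assignment. The false difference is 2 × 0.329 × d. If they act whenever one arm is more likely, it is 2 × (2 × 0.7066 − 1) × d = 0.826d. Type I error is from 4,000 simulated trials per case with no true effect, all 142 analysed by an unadjusted t-test.

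| d | Certain only: difference, type I error | Any tilt: difference, type I error |
|---|---|---|
| 0.10 | 0.07 SD, 6% | 0.08 SD, 8% |
| 0.25 | 0.16 SD, 17% | 0.21 SD, 23% |
| 0.50 | 0.33 SD, 49% | 0.41 SD, 65% |

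These are ceilings for each d, because they assume steering at every opportunity.

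**The case against.** A reader might infer that the design makes a third of assignments certain for everyone, or that the results will be biased. The documents support neither. The certainty exists only for someone who follows earlier assignments in order within a stratum. That the same individuals screen, consent and announce is an inference from a shared role label and two listed roles; the protocol does not say it. Nor does it say that study staff schedule the classes: item 8 leaves class times to the participants and the community health worker.

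The route to steering is also narrower than free choice of patients. Item 7 makes referral by community health workers the preferred route, and patients answering a flyer call in themselves. In the mail route only about a third are expected to answer, and half of those to agree. Consent forms go out first, with staff following up later, about a week later in the flyer routes. Matching a chosen patient to a chosen place across such delays is difficult. But the staff's follow-up call remains the step at which timing can vary, so the route is reduced, not closed.

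The payments ($599 against $100) and the hours fall on the participant; nothing shows that staff gain from steering. Item 25 models change from baseline and adjusts for covariates. That would help with measured differences, but not with unmeasured engagement. In item 8 the pre-survey is the first activity within each arm, after the arm is announced, so it is not a clean baseline for detecting the problem.

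A concealment procedure may sit in a document not shown. It could prevent staff from seeing the list, but not from inferring the next place from a published block size and the arms they have already announced.

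**Conclusion.** The concern holds as a conditional risk. For a team member who tracks assignments by stratum, 33.3% of assignments in a full block are known in advance (about 32.9% over 36 + 106), and about 71% can be guessed. This rests on staff seeing the assignments in order, which their task of announcing the arm makes likely, and on the absence of any described blinding of staff.

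Whether bias would follow, and how large, cannot be read from the documents; the type I error figures depend entirely on the assumed steering. It is nonetheless worth correcting before enrolment, because the change is cheap and this kind of bias cannot be reliably removed in the analysis.

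**What to change.** Both parts are needed, the first being the more important.

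1. **Separate the list from recruitment.** State in item 8 that the biostatistician, who is given no recruitment task in the protocol, generates and holds the list. REDCap releases each assignment only after consent, the demographic survey and the pre-survey have been saved for that patient. Item 10c gives the coordinator and research assistant access to the data and codes, so the list itself must be closed to them. That CDU's REDCap can be set up this way is an assumption.
2. **Vary the block size.** Replace the single size of 4 with randomly varying sizes (e.g. 4, 6 and 8) within each race/ethnicity stratum, and keep the sizes out of any document that recruiting staff use.

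**Cost.** A stratum that ends midway through a block of 8 can be unbalanced by up to four patients, hence up to eight overall if both strata tilt the same way. The present scheme does not guarantee Table 3's 53/53 either: 106 is not a multiple of 4, so that stratum can already differ by two. The pre-survey moves ahead of notification of the arm, which means editing the sequence in item 8 for both groups. Item 10a places the demographic survey at the end of the study, whereas items 8 and 9 place it at enrolment; this must be reconciled if that survey is to precede assignment. The sample size does not change.

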We will need to enroll at minimum total of 128 participants to successfully complete the study, with a breakdown of 32 African American and 96 Latinx patients to reflect the LACDHS patient population in our study.

Our community partner and Multiple PI (MPI) [name], along with the LACDHS Vaccine Hesitancy Outreach Group, will generate a list of LACDHS patients who have been offered an appointment to be vaccinated and who have not taken the COVID-19 test and/or vaccine, and who meet all other inclusion criteria. The patient list from the DHS Vaccine Hesitancy Outreach Group, is a filtered list of the empaneled patients we obtained from Aim 1. The patient list provided by the DHS Vaccine Hesitancy Outreach Group a list of current patients from DHS County records showing which patients who do not have a completed vaccination status on their record.

Our study staff ([name], project coordinator and [name], research assistant), will work with the support of our two consultant-specialist LACDHS CHWs, who will provide additional insight on recruitment strategies.

For our recruitment process: The two CHW specialists and the intervention CHWs will help us identify and recruit participants by assisting in circulating the patient recruitment flyer within their CHW networks and DHS facilities. By using the CHW’s existing CHW and DHS network, it can assist with quick identification and recruitment of vaccine-hesitant patients. CHWs who work with these identified vaccine-hesitant patients can talk to the patients about the study and validate our research project is a legitimate study to overcome any initial patient skepticism.

The study team will work with the Intervention CHWs and CHW specialists, and follow a standardized referral process. By having a standardized referral process with the CHW network, CHWs can assist with a soft hand off for patients that are interested in learning more about the study. Using CHWs in the referral process can also assist the study team, where the

CHWs can measure and assess the patients' interest in wanting to join the study and help with patient retention.

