Once the project is completed, both groups will be asked to complete a Common Data Element Survey as requested by the NIH's terms and conditions. A priority of the RADx initiative is to build the RADx Data Hub, the NIH's resources of RADx-generated research data that can help other researchers and public health officials better understand the impact of the COVID-19 pandemic, including outcomes, disparities, and possible solutions. RADx-UP projects collect data for the RADx Data Hub and simplify the analysis of that data, the NIH defined a set of Common Data Elements (CDEs). The NIH RADx-UP CDEs provide a standard set of study questions that RADx-UP projects are required to use in their COVID-19 studies. Additional information can be found at <https://radx-up.org/learning-resources/cdes/>

9. Surveys, questionnaires, or psychological tests: If your study uses surveys, questionnaires, or psychological tests, please list and describe the setting, mode of administration, the length of administration time, number of repeats, and if special training or qualifications are necessary to administer the study instruments. Describe provisions for maintaining privacy and confidentiality.

All the following surveys and questionnaires will be comprehensible to participants by ensuring readability checks on the type of language used, simplicity of language, and additional explanation of concepts.

A basic demographic survey (**see attached: Basic Demographic Survey**) will be administered on a phone call when the patient has been consented and enrolled in the study. In this demographic survey, the survey consists of demographic questions such as age, race and ethnicity, education level, and other sociodemographic questions and will take about 10 minutes to complete.

Pre- and post- surveys (**see attached: Pre- and Post- RADxUP Survey**) will be administered telephonically by study staff to enrolled study participants. These surveys will be provided to both control and case arms, to measure three key measures: trust, self-efficacy,

and intent to participate in COVID-19 testing and vaccination. Secondary measures included will use brief measures from the RADxUP and Phenx database of COVID protocols such as worry about COVID-19, knowledge, attitudes, behaviors, social support, perceived COVID-19 threat, and sources of information about COVID-19.

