- **Pre- surveys** will be administered by IRB-approved study staff, after study participants are consented and enrolled into the study and at a convenient time for the study participant. The survey should take about 30-60 minutes to complete (**see Pre- and Post- RADxUP Survey**). The survey questions and answers will be sent via email or mail prior to the phone call, and read and answered over the phone by the study staff to overcome any misinterpretation of the survey questions. The participant's response will be input by the study staff directly into REDCap under the subject ID#. No special training will be required to administer the survey.
- **Post- surveys** will take between 30-60 minutes to complete (**see Pre- and Post- RADxUP Survey**). The survey questions and answers will be read and answered over the phone by study staff to overcome any misinterpretation of the survey questions. The participant's response will be input by the study staff directly into REDCap under the subject ID#. No special training will be required to administer the survey.
 - o The post survey will be administered by study staff telephonically (similar to the pre-survey process) after:
 - Control arm – 6 weeks from the first survey
 - Case arm – after they complete the 6th group class and 6th personal phone call with the CHW

As part of the intervention arm, the modules will incorporate weekly formal “Knowledge Checks” (**see Knowledge Checks**) a comprehension questionnaire administered via email survey (sent by REDCap) sent after each module, which all participants will complete before their personal phone call with the CHW. The purpose of these Knowledge Checks is for the study team to measure patients' comprehension after each group session and throughout the course of the study. If patients score low in the Knowledge Checks, the CHW will review with the patients during their personal sessions to increase comprehension of the materials presented during the group session. There will be a total of 5 Knowledge Checks for Modules 1-5 (the Post- survey will be administered in lieu of a Knowledge Check for Module 6), each with 5-10 multiple-choice questions.

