Post- survey – like the pre- survey, the post- survey will be administered telephonically with study staff, at a time that is convenient for the study participant. The study staff, who are IRB approved, will resend the survey out before the phone call to read the questions and answer choices aloud and input the participant's answer directly into REDCap under the Subject ID#. Participants enrolled in both control and case arm will complete this survey. Participants in the control arm will complete the post- survey 6 weeks after they complete the pre- survey. Participants in the case arm will complete the survey after they attend the 6th group class and 6th phone call with the CHW.

Knowledge checks – this survey will only be administered to study participants randomly assigned to the case arm on a weekly basis, after they attend a group session. The survey will be sent out via email using the REDCap survey feature. If participants are not able to complete the survey via email, study staff will follow up with the participants via phone call to complete the survey where study staff will read the questions and answers aloud. The

study staff will then enter the answers directly into REDCap. This survey will need to be completed before the participants complete their personal phone calls with the CHW.

Patient encounter forms – this data collection tool will only be used on study participants randomly assigned to the case arm during their weekly teleconsultations. Intervention CHWs will complete these forms after each of their teleconsultations (personal phone calls) with their assigned study participants and enter their notes on REDCap. Each participant will have six completed patient encounter forms in their subject file on REDCap by the end of the study. The teleconsultations will be scheduled at a time that is convenient for both the participants and the CHWs.

One of the MPI and software programmer will strip personally identifiable information from the clinic data and substitute with a random code (Subject ID#). A master code list will be created separately that will link the code with the patient. This master code list will reside in a separate file in REDCap.

b. Where will the data be stored and how will it be secured during the study?

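### The three self-reported key measures are collected by telephone by the same staff role that announces the arm and supports the intervention, and nothing masks the interviewer

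*Protocol*

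**What the plan says.** **Outcomes.** Protocol VI.9 gives the pre- and post-surveys to both arms "to measure three key measures: trust, self-efficacy" and intent to be tested and vaccinated.

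**Collection.** VI.9 has study staff conduct the post-survey by telephone: "The survey questions and answers will be read and answered over the phone by study staff to overcome any misinterpretation of the survey questions". It adds "The participant's response will be input by the study staff directly into REDCap under the subject ID", and "No special training will be required to administer the survey". VI.10 repeats the mode: "the post- survey will be administered telephonically with study staff, at a time that is convenient for the study participant". Participants are sent the survey before the call.

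**Other tasks of the same role.**
- After randomisation, "the study staff will notify the participant of which group they were assigned to" (VI.8, Intervention Design).
- Study staff train the Intervention CHWs (VI.8, Training of CHWs).
- Study staff and the principal investigators review the CHWs' encounter forms in order to give feedback (VI.8, Intervention Arm).
- Study staff phone intervention participants who cannot complete a Knowledge Check by email (VI.10).

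**Who they are.** In the recruitment section (VI.7) the study staff are a project coordinator and a research assistant.

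**Timing.** The control post-survey falls six weeks after the first survey. The intervention post-survey follows the sixth class and sixth CHW call, and replaces a Knowledge Check for the last module (VI.9).

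**Self-completion.** VI.10 lets participants complete the pre-survey alone through an emailed REDCap link. The post-survey paragraph says it works like the pre-survey, but then describes telephone administration only.

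**The concern.** Trust, self-efficacy and intent are opinions spoken to an interviewer, so an interviewer who knows the arm can influence them through tone, probing or how an unclear reply is coded. The participant may also give the answer that the study team seems to want. The role that conducts the interview also supports the intervention, and its contact with participants differs by arm. The intervention participant may have been telephoned by staff about earlier comprehension quizzes, and meets the post-survey in the slot where a sixth quiz would have come. The control participant has no such sequence.

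At stake is the comparison of the three key measures. If these influences differ by arm, they add to or subtract from the estimated effect. A larger sample would not remove them, and neither would the covariate adjustment in VI.25. The protocol itself fixes who collects the outcome and how, so this is not a detail left to a statistical analysis plan.

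**Working it through.** **1. Is the interviewer masked?** Four places where the plan could have provided masking:

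- *Staff roles.* VI.8, VI.9 and VI.10 give announcement of the arm and the post-survey to the same role. No text separates them.
- *Group labels.* Group 1 and Group 2 (VI.8) are labels for explaining randomisation to participants. They mask nobody.
- *Call trigger.* The trigger differs by arm (VI.9) and intervention start dates are staggered (VI.8), so the due date can itself reveal the arm.
- *REDCap.* Intervention participants have six encounter forms in their subject file (VI.10), and post-survey answers are entered under the same subject ID. Opening the file can reveal the arm.

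None of these masks the interviewer.

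**2. The plan's own figure.** Inputs from VI.25: 64 per arm, effect 0.5 SD, two-sided 5%, power 80%.

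- Noncentrality = d × √(n/2) = 0.5 × √32 = 0.5 × 5.657 = 2.828.
- Normal approximation: Φ(2.828 − 1.960) = Φ(0.868) = 80.7%.
- Noncentral t, 126 df: 80.1%.

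The stated 80% reproduces, so sample size is not at issue.

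**3. Sensitivity to a differential reporting bias.** The documents give no size for such a bias, so 0.1, 0.2 and 0.3 SD are assumed. The true effect is set to zero and b is the part of the bias that differs between arms.

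- Noncentrality = b × √32, with 126 df.
- Rejection = P(T > t₀.₉₇₅) + P(T < −t₀.₉₇₅).

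| b (SD) | Noncentrality | Two-sided rejection | Of which favours intervention | b as share of 0.5 SD |
|---|---|---|---|---|
| 0 | 0 | 5.00% | 2.50% | 0% |
| 0.1 | 0.566 | 8.68% | 8.10% | 20% |
| 0.2 | 1.131 | 20.23% | 20.12% | 40% |
| 0.3 | 1.697 | 39.15% | 39.13% | 60% |

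The table takes the bias to favour the intervention. It shows how sensitive the test is. It is not evidence that a bias of this size exists.

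**The case against.** **Both arms face the same interviewers.** Control participants are also recruited, consented, told their arm, surveyed by telephone and paid by the study ($100, against $599 in the intervention arm; VI.17). A desire to please is present in both arms, and whatever is common cancels. This stands: only the differential part biases the comparison. A reader might infer that the bias acts in one arm only, or that a positive result could not be told apart from it. The documents support neither.

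**Delivery is already separate from outcome collection.** CHWs lead the classes and personal sessions, and no text has a CHW conduct the post-survey. This also stands, and it would be wrong to say that the interviewers delivered the programme. What remains is a supporting role: training the CHWs, reviewing encounter forms and fallback calls. Those calls are not a weekly routine either, since Knowledge Checks go out by email and staff phone only when that fails.

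**A role is not a person.** The protocol does not say that one individual announces the arm and then interviews the same participant, and other approved staff may join. That is correct. But nothing prevents the overlap, and the recruitment section names only two people.

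**Some interviewer influence is limited already.** Participants receive the survey in advance, and the text has items read aloud. It does not say that interviewers explain items as they please. This reduces the exposure without removing it, because the answer is still given to, and entered by, someone who may know the arm.

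**Masking would be incomplete.** Participants know their arm and may reveal it, and a call list without the arm is not enough by itself, for the timing and REDCap reasons set out above. This stands and shapes the remedy.

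**Conclusion.** The concern holds in a limited form. As written, the plan lets an interviewer who knows the arm collect all three key measures, and it neither masks that interviewer nor separates the interview from announcing the arm. Interviewer and desirability effects may therefore differ between arms and could favour the intervention. The direction is plausible, not proven, and the size is unknown.

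The figures of about 9%, 20% and 39% rest on assumed differential biases of 0.1, 0.2 and 0.3 SD, no true effect, 64 analysed per arm and a two-sample t-test. A reader might take them as an estimate of the trial's false-positive rate. They are not, because nothing in the documents indicates a bias of that size.

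The change is worth making because the unmasked interviewer is the avoidable part and costs little to remove. The comparison remains possible without it, but a positive finding would be easier to question.

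**What to change.** Amend the post-survey text in VI.9 and VI.10 as follows.

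1. The staff member who tells a participant the arm, or handles that participant's Knowledge Check or CHW follow-up, does not conduct that participant's post-survey. The other existing staff member does.
2. The interviewer works from a scheduled call list and a REDCap view that show neither the arm nor arm-specific forms. The unmasked colleague prepares the due dates, so the trigger for the call is not visible.
3. The interviewer reads items and answer choices verbatim, asks participants at the start not to mention their group, and records any unmasking.
4. If self-completion through REDCap stays available for the pre-survey, offer it for the post-survey on the same terms in both arms, and keep each participant's mode the same at both time points.

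**Cost.** No new staff, participants or instruments are needed. REDCap access rights must be set up and a due-date list maintained. Scheduling becomes less flexible: if one person did all the interviews, 128 post-surveys at 30 to 60 minutes come to 128 × 0.5 = 64 to 128 × 1 = 128 hours. Some unmasking and some participant desirability bias will remain, because participants cannot be masked in this design.
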